10 IMP DISCONTINUATION AND WITHDRAWAL

In accordance with the Declaration of Helsinki, the International Council for Harmonisation (ICH) Harmonised Guideline: Integrated Addendum to ICH E6(R1): Guideline for Good Clinical Practice (GCP) E6(R2), the FDA regulations relating to GCP and clinical trials, the EU Clinical Trials Directive, the EU GCP Directive and/or other applicable regulations, a patient has the right to withdraw from the trial at any time and for any reason, with no obligation to provide a reason, and without prejudice to his or her future medical care by the physician or at the institution.

The patient must be permanently discontinued from treatment if any of the following apply:

- Administrative decision by the investigator, GW, or a regulatory authority.
- Pregnancy.
- Protocol deviation that is considered to potentially compromise the safety of the patient.
- Withdrawal of patient assent.
- Withdrawal of parent(s)/legal representative consent.
- ALT or AST $> 3 \times$ ULN with the appearance of fatigue, nausea, vomiting, right upper quadrant pain or tenderness, fever, rash, and/or eosinophilia ($> 5\%$).
- ALT or AST $> 8 \times$ ULN.
- ALT or AST $> 5 \times$ ULN for more than 2 weeks.
- ALT or AST $> 3 \times$ ULN **and** (TBL $> 2 \times$ ULN **or** INR > 1.5).

Note: Prior to treatment discontinuation for the transaminase elevations noted above, the investigator may choose to confirm the transaminase elevations by repeating the following laboratory tests within 24–48 hours: ALT, AST, TBL, INR, % eosinophils, gamma-glutamyl transferase and alkaline phosphatase.

Should the above transaminase elevation criteria be confirmed, the patient must permanently discontinue the IMP. In cases where transaminase elevation IMP discontinuation criteria are not met or confirmed, the dose of IMP or a concomitant medication with known hepatotoxicity may be reduced. Dose adjustments should be discussed with the GW medical

Study Code: GWND18064

EudraCT Number: 2018-003370-27

Clinical Protocol 4.1, 07Jul2020 (duplicate synopsis removed)

monitor. The final decision regarding dose adjustments should be taken by the investigator.

- Lost to follow-up.

The patient may also be permanently discontinued from treatment for any of the following:

- Patient or caregiver non-compliance.
- AE (including clinically significant laboratory result) which, in the opinion of the investigator, would compromise the continued safe participation of the patient in the trial.
- Did not meet eligibility criteria.
- Any evidence of use of drugs of abuse or drug diversion.
- Suicidal ideation or behavior during the treatment period.

Patients who discontinue IMP should have their dose of IMP gradually reduced (10% each day) over a period of 10 days, beginning at the time the decision is made to discontinue (unless inadvisable due to an AE). Patients should continue in the trial and continue to complete trial assessments and visits as per protocol. Patients who discontinue IMP and complete tapering of IMP prior to the completion visit, do not need to attend an End of Taper visit.

Should a patient request or decide to withdraw from the trial, all efforts must be made to complete and report the observations as thoroughly as possible up to the date of withdrawal. Patients withdrawing due to an AE should be followed up according to [Section 12.7](#). All information should be reported on the applicable eCRF pages (refer to [Section 9.2](#)). All assessments required at the withdrawal visit should be conducted if possible. If the tapered dose is administered, patients should return for Visit 10, if possible. Wherever possible, a safety follow-up visit should take place 28 days from the date of last dose of IMP (refer to [Section 9.1.2](#)). If the withdrawing patient declines to give a reason for withdrawal of consent, the investigator must respect the patient's wishes.

Study Code: GWND18064

EudraCT Number: 2018-003370-27

Clinical Protocol 4.1, 07Jul2020 (duplicate synopsis removed)

11 URGENT SAFETY MEASURES

The sponsor and investigator may take appropriate urgent safety measures in order to protect the patients of a clinical trial against any immediate hazard to their health or safety. If such measures are taken by the investigator, they must notify GW immediately or at least within 24 hours of awareness. GW will report urgent safety measures to regulatory authorities by telephone within 24 hours of awareness, wherever possible, and will provide a written report to the regulatory authorities and IRB/IEC within 3 days.

Study Code: GWND18064

EudraCT Number: 2018-003370-27

Clinical Protocol 4.1, 07Jul2020 (duplicate synopsis removed)

12 ADVERSE EVENT REPORTING

12.1 Definitions

12.1.1 Adverse Event

For the purposes of this trial an AE is defined as:

Any new unfavorable/unintended signs/symptoms (including abnormal laboratory findings when relevant), or diagnosis or worsening of a pre-existing condition, which occurs following screening (Visit 1) and at any point up to the post-treatment, final safety follow-up visit (Visit 11), which may or may not be considered to be related to the IMP. Any event that is the result of a trial procedure must be recorded as an AE.

Surgical/Investigational procedures are not AEs. The medical reason for the procedure is the AE. Elective hospitalizations for pre-trial existing conditions or elective procedures are not AEs. The exception may be if the patient has an AE during hospitalization which prolongs their scheduled hospital stay in which case it would be considered a SAE (refer to [Section 12.2](#)).

If reporting a fatal event, the SAE term should be the underlying cause of the death (e.g., disease or medical condition leading to death).

12.1.2 Investigator

The term investigator refers to the trial PI or a formally delegated trial physician.

12.2 Serious Adverse Events

During clinical investigations, AEs may occur which, if suspected to be IMP-related, might be significant enough to lead to important changes in the way the IMP is developed (e.g., change in dose, population, monitoring need, consent/assent forms). This is particularly true for events that threaten life or function. Such SAEs will be reported promptly to regulatory authorities, applicable IRBs/IECs and investigators (expedited reporting) by GW.

An AE must only be classed as serious, i.e., a SAE, when the event falls into 1 of the following criteria:

- Results in death.
- Is life-threatening*.

Study Code: GWND18064

EudraCT Number: 2018-003370-27

Clinical Protocol 4.1, 07Jul2020 (duplicate synopsis removed)

- Requires inpatient hospitalization or prolongation of existing hospitalization.
- Results in persistent or significant disability/incapacity.
- Is a congenital anomaly/birth defect.
- Is medically significant^{**}.

^{*} The term “life-threatening” in the definition of “serious” refers to an event in which the patient was at risk of death at the time of the event; it does not refer to an event which, hypothetically, might have caused death if it were more severe.

^{**} Medical and scientific judgment should be exercised in deciding whether SAE reporting is appropriate in other situations. Important medical events may not be immediately life-threatening or result in death or hospitalization but may jeopardize the patient or may require intervention to prevent one of the other outcomes listed in the definition above. These should also usually be considered serious. Examples of such events are intensive treatment in an emergency room or at home for allergic bronchospasm, blood dyscrasias or convulsions that do not result in hospitalization, or development of drug dependency or use of drugs of abuse.

12.3 Reporting Procedures for Serious Adverse Events

All SAEs occurring during the trial must be reported to GW with any other supporting information and recorded in the AE section of the eCRF. Any ongoing SAEs should be followed up until resolution wherever possible. For all deaths, the working diagnosis or cause of death as stated on a death certificate, available autopsy reports and relevant medical reports should be sent to GW promptly.

All SAEs must be recorded in the eCRF within 24 hours of discovery or notification of the event. GW PVD will be automatically notified that an SAE has been recorded. Any additional information required for a case (follow-up or corrections to the original case) will be requested by GW PVD through eCRF queries.

The investigator should continue to document all AEs which occur up to the last formal follow-up observational period (Visit 11). If the investigator subsequently becomes aware of any deaths or a new IMP-related SAE after the last formal follow-up period of the trial, these should still be reported to the GW PVD.

Any other problem discovered after Visit 11 which is deemed to be an unexpected safety issue and is likely to have an impact on patients who have taken part in the trial must be

Study Code: GWND18064

EudraCT Number: 2018-003370-27

Clinical Protocol 4.1, 07Jul2020 (duplicate synopsis removed)

treated as an SAE and reported to the GW PVD. Such post-trial SAEs do not need to be recorded on the patient's eCRF if editing rights to the eCRF have been removed due to final trial data lock. GW PVD may request safety follow-up information after the final trial visit in order to investigate a potential safety issue.

Contact details for the GW PVD are provided at the front of the site files for all trial sites.

12.4 Pregnancy

Any female patient who has become pregnant whilst receiving IMP, or within 90 days of last dose of IMP, must be reported to the GW PVD. Where possible the investigator should provide the outcome of the pregnancy.

All pregnancies must be recorded in the eCRF within 24 hours of becoming aware. GW PVD will be automatically notified that a pregnancy has been recorded. Any additional information required for a case (follow-up or corrections to the original case) will be requested by GW PVD through eCRF queries.

The investigator is not obliged to actively monitor for any pregnancies that commence more than 90 days after the final dose of IMP. However, if the investigator becomes aware of a new pregnancy outside this time limit then they should report it as above. The GW PVD will follow up for all pregnancy outcomes.

12.5 Causality Assessment

Causality assessment is required for all AEs and SAEs. Causality assessment must only be assigned by the investigator. All cases judged as having a reasonable suspected causal relationship to the IMP must be reported as such. The expression "*reasonable causal relationship*" is meant to convey in general that there are facts (evidence) or arguments to suggest a causal relationship.

The following question which must be answered by the investigator for all AEs is used to capture the reasonable causal relationship of an event to the IMP:

"In your opinion is there a plausible relationship to the IMP?" The answer is either "yes" or "no".

Events that start before the first dose of IMP (pre-treatment) should be considered as not causally related. Where a pre-treatment event worsens in severity following the first dose of IMP, a new event record should be entered into the eCRF.

Study Code: GWND18064

EudraCT Number: 2018-003370-27

Clinical Protocol 4.1, 07Jul2020 (duplicate synopsis removed)

Considering the explanation given above, investigators are strongly encouraged to express their opinion on what the cause of an AE might be. For individual patients, the investigator is usually in the best position to assess the underlying suspected cause of an AE. For all AEs and especially SAEs, it is important that the investigator assess not only the possible role of the IMP but also other potential contributing factors. Factors for consideration of the underlying cause may include:

- Medical and disease history.
- Lack of efficacy/worsening of treated condition.
- Concomitant or previous treatment.
- IMP discontinuation.
- Protocol-related procedure.

12.6 Reporting Procedures for All Adverse Events

All AEs (including SAEs) occurring during the trial will be reported on the running logs in the AE section of the eCRF. This includes all events from the time following screening (Visit 1) up to and including the post-trial follow-up visit (Visit 11), whether or not attributed to IMP and observed by the investigator or patient.

For the patient's expected seizure types, these do not routinely require documentation as AEs. However, any worsening, including change in the pattern or severity of seizures should be documented in the eCRF if deemed to meet the definition of an AE, in the investigator's opinion.

Any AE which meets SAE criteria should still be reported as a SAE.

The following information will need to be provided for all AEs:

A) Adverse Event (Diagnosis or Syndrome if Known, or Signs and Symptoms)

Where the investigator cannot determine a diagnosis, signs or symptoms should be recorded in the AE section of the eCRF. Once a diagnosis has been determined the AE section of eCRF must be updated to reflect the diagnosis in replacement of the original symptoms. In circumstances where only a provisional diagnosis is possible (working diagnosis), the eCRF must be updated to reflect the provisional diagnosis in replacement of the original symptoms. In some circumstances it may be relevant for the investigator to include the symptoms alongside the diagnosis in the verbatim event description.

Study Code: GWND18064

EudraCT Number: 2018-003370-27

Clinical Protocol 4.1, 07Jul2020 (duplicate synopsis removed)

However, the diagnosis (full or provisional) should be clearly stated, e.g., fever and malaise due to respiratory tract infection.

B) Adverse Event Start Date and Stop Date

The start and stop dates of the event must be provided. All AEs require these fields to be completed in full. Partial dates or missing dates are not normally acceptable and significant effort must be undertaken to obtain any unknown information. If a precise date is not known an estimated date should be provided instead. When a complete date cannot be given, record as much information as possible (i.e., month and year or, in exceptional circumstances, just year). When the actual start date becomes known the eCRF must be updated to replace the previously recorded date.

C) Outcome

The outcome of the event must be recorded accurately and classified into 1 of the following categories:

- Recovered.
- Recovered with sequelae.
- Continuing.
- Patient died.

D) Severity

When describing the severity of an AE the terms mild, moderate, or severe should be used. Clinical judgment should be used when determining which severity applies to any AE.

If the severity of an AE fluctuates day-to-day, e.g., a headache or constipation, the change in severity should not be recorded each time; instead, only the worst observed severity should be recorded with AE start and stop dates relating to the overall event duration, regardless of severity.

A severe AE is not the same as a SAE. For example, a patient may have severe vomiting, but the event does not result in any of the SAE criteria above. Therefore, it should not be classed as serious.

E) Causality

See [Section 12.5](#) above.

Study Code: GWND18064

EudraCT Number: 2018-003370-27

Clinical Protocol 4.1, 07Jul2020 (duplicate synopsis removed)

F) Action Taken with Trial Medication

This question refers to the action taken with the IMP due to an AE. The action with the IMP must be classed as:

- Not applicable, patient is not taking IMP.
- Dose not changed.
- Dose reduced.
- Trial medication interrupted.
- Trial medication stopped.

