8.1.2 Dose Escalation and Dose Adjustments

The daily volumes of IMP solution to be taken will be calculated based on the patients' weight and the dosing schedule will be provided to the caregiver. Further information on dispensing procedures will be provided in a separate Pharmacy Manual.

Caregivers will be trained on dose administration at Visit 2 (Day 1). Each patient will take their first dose of IMP at the clinic at the end of Visit 2 (Day 1). The investigator

Study Code: GWND18064

EudraCT Number: 2018-003370-27

Clinical Protocol 4.1, 07Jul2020 (duplicate synopsis removed)

will observe IMP administration by the caregiver at Visit 2 and verify that IMP was correctly administered, and that the patient did not aspirate. If an unacceptable AE develops at any time during the dose escalation period(s), dosing should initially be suspended or amended, at the investigator's discretion and in a blinded manner, until the event has resolved or is well tolerated. Patients who have escalated above 5 mg/kg/day should return to the previous dose level tolerated in steps of 5 mg/kg/day each week, unless a faster reduction is judged to be required for safety reasons. If a patient cannot tolerate 5 mg/kg/day, doses should be reduced to 2.5 mg/kg/day. If necessary, dosing may be temporarily suspended.

Patients whose dose has been decreased can have their dose increased again, if the tolerability improves. Patients unable to tolerate the target dose may stay at a lower dose. However, if a patient cannot tolerate a dose of 2.5 mg/kg/day the patient should permanently discontinue IMP treatment, unless a lower dose level is agreed in discussion with the medical monitor and can be accurately measured (minimum single dose volume 0.1 mL). Dose adjustments should be discussed with the GW medical monitor. The final decision regarding dose adjustments should be taken by the investigator. During the maintenance period, patients should continue on a stable dosing regimen at the target dose level. If that dose becomes poorly tolerated, the investigator may consider temporarily or permanently reducing the dosage for the remainder of the maintenance period; dose adjustments should follow the guidance above. However, where possible, the patient should be encouraged to return to the target dose level.

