Transaminase elevations should be medically managed by the investigator either by reducing the IMP dose as described above or, following discussion with the medical monitor, by reducing concomitant medications judged to be causing the elevation (as per [Section 8.2](#)). Dose adjustments should be discussed with the GW medical monitor. For potential cases of drug-induced liver injury see [Section 12.8](#).

Patients will escalate IMP to the target dose level for their dose group over a period of up to 2 weeks depending on the target dose (e.g., no titration is required to 5 mg/kg/day while titration to 15 mg/kg/day takes 2 weeks [weekly increments of 5 mg/kg/day] as indicated in [Table 8.1.2-1](#)). Following escalation patients will remain at their assigned target dose level for the duration of the maintenance period of the trial.

Study Code: GWND18064

EudraCT Number: 2018-003370-27

Clinical Protocol 4.1, 07Jul2020 (duplicate synopsis removed)

Table 8.1.2-1 Dose Escalation Regimen

Day	Dose GWP42003-P (mg/kg/day)*
1-7	5
8-14	10
15	15

* IMP is to be taken twice daily. Total daily doses are shown. The placebo group will take matching volumes of placebo.

After completion of dosing, patients who do not immediately enter the OLE study (under a separate protocol) at Visit 9 will have their dose of IMP tapered gradually, an average of 10% of per day, over a period of 10 days (the taper period may be shorter if the patient enters the OLE during the taper period). Patients who reach the minimum single dose volume of 0.1 mL should remain at that dose until they complete the taper period. A taper schedule will be provided for each patient.

Patients who discontinue from treatment early should also taper the IMP (unless continued dosing is inadvisable, e.g., due to an AE). The decision whether to taper IMP or not will be left to the investigator's clinical judgment.

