#### **6.1.9.1 Adverse events**

A TEAE is defined as an AE with a start date on or after the first dose of IMP. If an AE has a partial start date and it is unclear from the partial date (or the stop date) whether the AE started prior to or post first dose of IMP then the AE will be considered treatment emergent. If the start date of the AE is the same as the date of first dose of IMP then the AE will be considered treatment emergent.

A TEAE will be considered treatment-related if the plausibility relationship to IMP is recorded on the eCRF as ‘yes’. If the data on plausibility relationship to IMP is missing then the TEAE will be considered treatment-related.

A TEAE will be considered leading to permanent discontinuation of IMP (leading to withdrawal) if the action taken with IMP is recorded on the eCRF as ‘trial medication stopped’ or the outcome is recorded on the eCRF as ‘patient died’.

A treatment-related TEAEs leading to withdrawal is a TEAE leading to permanent IMP

discontinuation and considered treatment-related as per above definition.

A TEAE will be considered leading to IMP temporary discontinuation if the action taken with IMP is recorded on the eCRF as 'trial medication interrupted'.

A TEAE will be considered leading to permanent IMP dose reduction excluding permanent discontinuation if the action taken with IMP is recorded on the eCRF as 'dose reduced'.

An AE will be considered fatal if the outcome is recorded on the eCRF as 'patient died'.

The time to first onset of AE will be calculated for TEAEs as:

Start date of AE – Date of first dose of IMP + 1

The time to AE resolution will be calculated for TEAEs as:

Stop date of AE – Start date of AE + 1

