### **7.4 Exposure and Compliance**

IMP is to be administered twice daily (morning and evening). The first dose will be taken in the clinic on Day 1. The date of final dose in the treatment period will be recorded on the eCRF. The date of final dose, for patients who enter the taper period, will be recorded on the eCRF at the end of taper visit.

For dosing during the treatment period, the following data will be presented: total number of dosing days, number of days with diary reported, number of days with doses not taken according to the diary will be reported as continuous variables. Number and percentages of dose adjustments (escalation, decrease, other) as well as methods of IMP administration will be described.

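### An adverse event handled only by withholding the next titration step has no matching action-taken category, so its link to missing the target dose is lost

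*Protocol*

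**What the plan says.** **The coding list.** Protocol Section 12.6 F states: "This question refers to the action taken with the IMP due to an AE. The action with the IMP must be classed as" one of five options: not applicable because the patient is off treatment, "Dose not changed", reduced, interrupted, or stopped. There is no free category.

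**The titration.** Under Protocol Section 8.1.2, "no titration is required to 5 mg/kg/day while titration to 15 mg/kg/day takes 2 weeks". Table 8.1.2-1 puts the increases at Day 8 (to 10 mg/kg/day) and Day 15 (to 15 mg/kg/day). If an unacceptable AE occurs during escalation, "dosing should initially be suspended or amended", and "Patients who have escalated above 5 mg/kg/day should return to the previous dose level tolerated in steps of 5 mg/kg/day each week". After a sentence on raising the dose again following a decrease, the section adds: "Patients unable to tolerate the target dose may stay at a lower dose".

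**The analysis.** SAP Section 6.1.9.1 reads the action-taken field: "A TEAE will be considered leading to permanent IMP dose reduction excluding permanent discontinuation if the action taken with IMP" is the reduced option. The interrupted option gives temporary discontinuation. The stopped option, or a fatal outcome, gives permanent discontinuation. SAP Section 9.1 lists AE tables for discontinuation and for dose reduction, but none for an escalation that did not take place. SAP Section 7.4 adds an exposure summary, "Number and percentages of dose adjustments (escalation, decrease, other"), with no reference to AEs.

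**The concern.** Each option in the list compares the dose after the AE with the dose before it. During titration the relevant comparison is with the dose that was scheduled next. A patient who remains at 10 mg/kg/day because of an AE has had no reduction, interruption or stop, yet receives 10/15 = 67% of the target. At 5 mg/kg/day the figure is 5/15 = 33%, which is the dose of the low-dose arm.

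This can arise only where an increase is planned, so only in the 15 mg/kg/day active group and the placebo group on matching volumes. Protocol Section 3.3.2 includes 5 mg/kg/day partly because it might be better tolerated, and Section 13.6.3.2 presents the dose groups separately so that dose effects on safety can be explored. In the 5 mg/kg/day groups, an AE that changes dosing has a category. In the 15 mg/kg/day groups, one type of AE-driven dosing consequence does not.

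**Working it through.** The plan states no figure on this point, so the check traces each course of events from the list in Protocol 12.6 F to the flags in SAP 6.1.9.1.

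| Course after an AE during titration | Category that fits | Flag under SAP 6.1.9.1 |
|---|---|---|
| Dosing suspended, later resumed, target not reached | Interrupted | Temporary discontinuation |
| At 10 mg/kg/day, stepped back to 5 | Reduced | Permanent dose reduction |
| Treatment ended | Stopped | Permanent discontinuation |
| Dosing continues at 5 or 10 mg/kg/day, next step not taken | Unchanged, by elimination | None |

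Only the last row is uncovered. Three other outputs were checked to see whether they restore the link:

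- *Exposure (SAP 7.4).* It counts adjustments. A step not taken is an adjustment that did not occur, and no reason or AE is attached. The section does not ask for the number of patients reaching target dose.
- *Titration-period and onset-time AE counts (SAP 9.1).* These show when an AE began, not what it did to dosing.
- *Safety analysis set (SAP Section 5).* A patient assigned to and taking cannabidiol stays in the assigned dose group. A patient held at 5 mg/kg/day is therefore reported in the 15 mg/kg/day column.

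**Patients who could be affected.** Protocol Section 13.1 plans 84 patients per active group and 42 per placebo group. With a planned escalation: 84 + 42 = 126 of 252, or 50%.

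**Illustrative size in the active group.** Let *p* be the assumed proportion held by an AE, and *q* the assumed share of those that are pure holds coded as unchanged. Patients without the link = 84 × *p* × *q*.

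| *p* | *q* = 0.5 | *q* = 1 |
|---|---|---|
| 0.05 | 2.1 | 4.2 |
| 0.10 | 4.2 | 8.4 |
| 0.20 | 8.4 | 16.8 |

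Neither *p* nor *q* is in the documents. The table shows the scale under stated assumptions and is not an estimate.

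**The case against.** A reader might infer that every AE that keeps a 15 mg/kg/day patient below target disappears from the AE dose-action tables. The documents do not support that. Suspension or amendment is the stated first response to an unacceptable AE during escalation, and patients above 5 mg/kg/day are to return to the last tolerated level. Suspension and step-back have categories and flags. The sentence that lets patients stay at a lower dose also follows text on dose decreases, so some of those patients will already have a reduction recorded.

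Four further points against a stronger reading stand:

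- The coding of a hold is inferred by elimination. The eCRF completion instructions are not among the documents, and a site could enter a reduction relative to schedule. That would preserve the link at that site, but without a rule the sites need not agree.
- SAP 9.1 lists tables for temporary dose reductions and for dose reductions overall, but 6.1.9.1 gives a derivation only for permanent ones. Absence from every AE dose-action table therefore cannot be shown from the text. What can be shown is absence from the flags that are defined.
- The AE remains in the overall, treatment-related, severity and titration-period tables and in the listings with start and stop days. A general claim that 15 mg/kg/day would look better tolerated goes too far; any understatement is confined to the dose-action summaries.
- Failure to reach target dose is not among the listed safety endpoints, and the RSBQ comparison is untouched. SAP Sections 1 and 9.5 record that the trial was discontinued and that the analysis is descriptive, so 84 is a planned figure and actual counts may be smaller.

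None of this supplies a category for the pure hold or restores its link to dosing.

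**Conclusion.** The gap is real and narrow. An AE during titration that is managed only by not taking the next planned step has no matching category in Protocol 12.6 F. By elimination it would be coded as unchanged, and SAP 6.1.9.1 would not flag it. The AE itself is still reported; its connection with failure to reach target dose is not.

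The size is unknown. Under the assumptions above (5% to 20% of 84 planned patients held by an AE, half to all of them pure holds) it is about 2 to 17 patients, or 2.5% to 20% of the group. The AE dose-action rate would be understated by that much only if none of these patients had another AE-related dose action. No hypothesis test or efficacy result depends on it. This is a cheap improvement to the by-dose tolerability description, not an error that undermines the plan.

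**What to change.** Add a category to the list in Protocol 12.6 F: *planned dose escalation delayed or not done*. Define the matching treatment-emergent AE group in SAP 6.1.9.1. Add one summary in SAP 9.1 for the 15 mg/kg/day active group and the 15 mg/kg/day-volume placebo group. The SAP already splits placebo by volume for safety, so the columns exist.

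With the trial discontinued, the eCRF may no longer be open to change. In that case, derive a flag: dose below the scheduled level at Day 8 or Day 15, with an AE ongoing on that day. Take the dose from the dose-adjustment record where possible. The diary asks whether dosing followed the schedule and asks for a volume only if it did not, so it may not show a hold once a revised schedule has been issued.

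The cost is one eCRF option or one programmed variable, and one table. The derived flag shows association in time and should be labelled so, because it may pick up unrelated AEs. Restricting it to AEs recorded as plausibly related would reduce that. The change affects reporting only and leaves every dosing rule as it is.
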